### **1.2.2 Potential Benefits**

No immediate benefits are available to the subject.

Potential benefits to the subject are related to the long-term outcome of these studies. If the pathogenic mechanisms for GI inflammatory diseases can be further dissected, more specific diagnostic and appropriate therapeutic measures can be developed. Specifically, this study will expand the knowledge as to the role of eosinophils and eosinophil-derived granule proteins in gastrointestinal inflammation. In addition, these studies will provide the basis for future diagnostic criteria and treatments for certain GI inflammatory diseases.

Treatment of EoE is in large part administered to prevent the development of esophageal stricture. However, we are extremely limited in the available clinical parameters to monitor disease progression in this regard. The overall aim of this proposal is to evaluate the association between patient reported symptoms, esophageal function and eosinophil activity using standard and investigative assessment tools. This data will advance our understanding of the relationship between patient reported symptoms, esophageal inflammation and esophageal function and provide novel information regarding the utility of potentially less invasive disease assessment tools. Second, there is the potential to gain further understanding of the pathogenesis of disease. Future studies will use tools identified here to define the natural history and measure response to treatment.

*Taken together, results from these studies will provide a rich assessment of the esophageal mucosa using a minimally invasive device, the EST. We anticipate that EST protein measurements will correlate with symptoms, inflammatory proteins and a functional biometric. We will take advantage of the robust resources and rich collaboration of three academic institutions to address these aims.*

## 2 OBJECTIVES

### 2.1 Study Objectives

**Specific Aim 1:** Do eosinophil proteins captured by the EST correlate with symptoms related to pediatric EoE?

Prior to children undergoing a standard of care endoscopy and biopsy, we will assess their symptoms with a validated score sheet (PEESS)(3). Then, they will swallow an EST and leave it in place for one hour. At the end of the hour, we will remove the EST and freeze it so that we can measure eosinophil proteins that stick to the EST at a later time. We will compare the symptoms score with the EST protein levels. Previous studies show variability in the correlation of symptoms with inflammation, but we anticipate that because the EST samples all of the esophagus, and not just a small piece, like the esophageal biopsy, the EST protein levels will correlate with symptoms (2).

**Specific Aim 2:** Do eosinophil proteins captured by the EST correlate with the markers of EoE pathogenesis?

In the same pediatric subjects described in Aim 1, we will obtain esophageal biopsies and measure the amount of inflammation in that tissue using 3 different specialized scoring systems (4-6). We will correlate these inflammation scores in the biopsy with the eosinophil protein levels from the EST. We anticipate that the inflammation scores from the tissue will correlate with the eosinophil protein levels on the ESTs.

**Specific Aim 3:** Do eosinophil proteins captured by the EST correlate with a measure of esophageal function?

In the same pediatric subjects described in Aim 1, we will perform EndoFLIP measurements during the endoscopy. The EndoFLIP is a slender probe covered by a smooth long balloon that is passed into the esophagus and slowly expanded with a salt solution (7). As the EndoFLIP is expanded, sensors inside the balloon identify pressure values that reflect how well the esophagus can stretch. Our early study shows that these readings can identify reduced distensibility in children with EoE (8). We will correlate distensibility measurements obtained by the EndoFLIP with the eosinophil protein levels from the EST.

### 3 STUDY DESIGN

When children are scheduled to undergo an endoscopy, research assistants will contact the family to arrange for the EST to be performed within one week of the endoscopy as previously described (REF). Prior to swallowing the EST, the patient will complete the PEES form to assess symptoms. The string will be left in place for 1 hour and then removed. The endoscopy and EREFs and EndoFLIP will be performed as previously described (2). Endoscopic severity: Endoscopic esophageal appearances will be scored using a validated EoE scoring system (EREFS). Five features of EoE will be scored: Edema (0-1), Rings (0-3) Exudates (0-2), Furrows (0-1), Stricture (0-1). Results will be reported as an inflammatory score (edema, exudates, furrows) and fibrostenotic score (rings, stricture). Functional Luminal Imaging Probe (FLIP): After endoscopic visualization, the FLIP, a 16 cm probe (Crospon) will be placed transorally and positioned 3 cm distal to the lower esophageal sphincter. Esophageal cross sectional areas and intrabag pressure will be measured during stepwise distensions beginning with 5 mL and increasing to a maximum of 70mL or intrabag pressure of 50 mmHg is achieved, whichever comes first. FLIP is FDA-approved without age restriction and its use has been approved by our IRBs previously. Primary results will be reported as distensibility plateau (mm).

EST and biopsy samples: The EST will be placed in a labeled tube and frozen until analysis as below. Four mucosal biopsies will be obtained from the distal esophagus for protein (3) and histological (1 biopsy) analysis. Samples for protein analysis will be snap frozen for batch processing and assessment. Samples for histological analysis will be paraffin embedded and cut into 5 $\mu$ M sections for batch staining.

## **4 STUDY ENROLLMENT AND WITHDRAWAL**

Children with EoE or symptoms of esophageal dysfunction concerning for EoE, who are 7 Years of age and older, will be enrolled in this study at Children's Hospital Colorado (CHCO) and Children's Hospital of Philadelphia (CHOP). Most children 7 years and older can swallow capsules. Subjects will be identified by screening appointment schedules, a well-tested method used at both institutions. Informed consent and assent will be obtained. After endoscopy, subjects will be identified as: 1) EoE active or 2) EoE inactive or 3.) other-symptoms but normal histology or vice versa. EoE will be defined based on current diagnostic criteria as having clinical symptoms of esophageal dysfunction, >15 eos/HPF, and other causes of eosinophilia ruled out either by negative pH/impedance study or greater than 6 weeks of treatment with proton pump inhibitor prior to endoscopy (1). EoE active will be defined as having symptoms and abnormal histology. EoE inactive will be defined as being asymptomatic and <15 eos/HPF. "Other" patients will be analyzed separately based on clinical diagnoses. Subjects will be age and sex matched for data analysis.

**Participation of Minorities:** Subjects will be recruited/enrolled without regard to racial/ethnic group.

**Participation of Children:** Children aged 7 years and older will be recruited/enrolled.

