## LIST OF ABBREVIATIONS

*{Please add all disease or study-specific abbreviations/acronyms in this section. Modify this list as needed for your particular study and remove abbreviations that are not used in the document.}*

AE	Adverse Event/Adverse Experience
CFR	Code of Federal Regulations
CHCO	Children's Hospital Colorado
CHOP	Children's Hospital of Philadelphia
CRF	Case Report Form
DCC	Data Coordinating Center
DSMO	Data and Safety Monitoring Officer
EOE	Eosinophilic Esophagitis
EREFs	Endoscopic Reference System
EST	Esophageal String Test
GCP	Good Clinical Practice
HIPAA	Health Insurance Portability and Accountability Act
ICF	Informed Consent Form
ICH	International Conference on Harmonisation
IRB	Institutional Review Board
ISM	Independent Safety Monitor
MOP	Manual of Procedures
N	Number (typically refers to participants)
NIH	National Institutes of Health
OHRP	Office for Human Research Protections
OHSR	Office of Human Subjects Research
PEESS	Pediatric Eosinophilic Esophagitis Symptom Scores
PI	Principal Investigator
QA	Quality Assurance
QC	Quality Control
SAE	Serious Adverse Event/Serious Adverse Experience
SOP	Standard Operating Procedure
US	United States

Title:	Use of Esophageal String Test to understand symptoms, inflammation and function in eosinophilic esophagitis
Overview:	Presently, the only method available to monitor disease activity in Eosinophilic Esophagitis is endoscopy with pathological review of biopsies. The overall goal of this study is to determine the ability of the Esophageal String Test (EST), a minimally invasive capsule based technology, to measure disease activity in children with EoE.
Objectives:	
Primary Aim: Do eosinophil proteins captured by the EST correlate with symptoms related to pediatric EoE?
 
Secondary Aim 1: Do eosinophil proteins captured by the EST correlate with the markers of EoE pathogenesis?
 
Secondary Aim 2: Do eosinophil proteins captured by the EST correlate with a measure of esophageal function?

Population:	40 subjects: males and females, ages 7-18 years old undergoing upper endoscopy for monitoring of EoE or for symptoms of esophageal dysfunction concerning for EoE
Study Sites:	
Lead Site: Children's Hospital of Colorado
 
Recruitment Site: Children's Hospital of Philadelphia
 
Clinical Laboratory: University of Illinois, Chicago

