## 1 INTRODUCTION: BACKGROUND INFORMATION AND SCIENTIFIC RATIONALE

### 1.1 Background Information

Eosinophilic Esophagitis (EoE) is a chronic disease characterized by symptoms related to esophageal dysfunction and large numbers of eosinophils in the lining of the esophagus (1). An endoscopy is required to make the diagnosis, because a biopsy of the esophageal tissue needs to be examined under the microscope. Eosinophils contain a number of proteins that likely participate in their function. Eosinophil peroxidase, major basic protein, eosinophil cationic protein and eosinophil derived neurotoxin are four of the major proteins that are associated with the eosinophil's function.

The EST is a capsule filled with a 90cm nylon string. A trailing end of the string protrudes from one end of the capsule. This end is taped to the cheek and the capsule is swallowed. As the capsule travels to the small intestine, the string inside the capsule is dislodged, leaving a string that goes from the cheek to the small intestine. The capsule dislodges from the string and the string is left in place, in the mouth, esophagus, stomach and small intestine for an hour. During this time, the string rubs against the inside of the esophagus and collects eosinophil proteins. After one hour, the string is removed through the mouth and placed in preservative to save the eosinophil proteins. The fluid extracted from the string is analyzed in the laboratory for eosinophil proteins. In a previous study, we showed that the eosinophil proteins captured by the string correlated with the number of eosinophils and amount of eosinophil proteins in the tissue biopsy (2). In this proposal, we will measure eosinophil proteins contained in the EST and correlate that with esophageal symptoms, inflammatory proteins and function.

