### 1.2 Rationale

Procurement of mucosal biopsies during sedated endoscopy is the only method to determine whether a child may have eosinophilic esophagitis (EoE). Counting esophageal eosinophils in the squamous epithelium remains key to establishing the diagnosis. To date, no blood, stool, breath or other peripheral sampling of eosinophil related biomarkers has been shown to correlate with mucosal eosinophilia in esophageal biopsies, thus leaving patients and families with the only option of undergoing this invasive, costly and time consuming procedure. Sedated upper endoscopy with biopsy is a safe procedure, but alternative methods that limit or eliminate exposure to anesthetic agents and address other problematic features are needed to obtain diagnostic samples. Although eosinophils are easy to count, variability exists with respect to reporting, and better biomarkers must be determined. In this regard, we, and others showed that effluents obtained from the esophageal lumen are reflective of esophageal eosinophilia. Katzka et al determined that the esophageal sponge is able to harvest mucosal scrapings to measure eosinophils (10). This approach is not suitable for children because of its size and tolerability. Our work documents that the Esophageal String Test (EST) can detect luminal biomarkers that reflect esophageal eosinophilic infiltration (2). This capsule based technology is well tolerated by children ages 7 years and up, and fluid adherent to the string has been shown to contain eosinophil granule proteins that correlate with esophageal eosinophilia and amounts of these proteins in biopsies.

The overall goal of this study is to discover a less invasive fashion to make the EoE diagnosis and assess disease activity in children. Here, we will determine whether eosinophil granule proteins captured by the EST correlate with: a) EoE symptoms, b) EoE histopathological scores and inflammatory proteins and c) a new functional biometric, distensibility. In this proposal, we hypothesize that luminal eosinophilic granule proteins will correlate with symptoms, inflammatory proteins and distensibility.

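### Section 4 sets aside children whose symptoms and histology disagree, while the aims and sample size point to correlations in all 40 completers; the analysis set for the primary EST-PEESS correlation needs to be named.

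*Combined protocol and SAP*

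**What the plan says.** Section 4 classifies each child after endoscopy. Active means symptoms together with abnormal histology. For the second class, "EoE inactive will be defined as being asymptomatic and <15 eos/HPF". The third class is "other-symptoms but normal histology or vice versa", and these children "patients will be analyzed separately based on clinical diagnoses". The same paragraph adds: "Subjects will be age and sex matched for data analysis".

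The analysis text does not take this up. Section 6.2 lists the correlations, beginning with EST analyte against PEESS, and Section 10 specifies Spearman's correlation. Neither says which children enter.

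Other places suggest that everyone does:
- The synopsis population is "40 subjects: males and females, ages 7-18 years old undergoing upper endoscopy for monitoring of EoE" or for symptoms that raise suspicion of EoE.
- Section 2.1 carries Aims 2 and 3 out "In the same pediatric subjects described in Aim 1".
- Section 4.3 plans for 40 children who complete all procedures.
- Section 10 bases 80% power at a correlation of 0.45 on 40 children.

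On how the EST relates to histology, Section 1.1 reports that in an earlier study "the eosinophil proteins captured by the string correlated with the number of eosinophils and amount of eosinophil proteins in the tissue biopsy". Section 1.2 likewise speaks of "eosinophil granule proteins that correlate with esophageal eosinophilia and amounts of these proteins in biopsies".

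**The concern.** The primary aim is a single correlation, between EST proteins and symptoms. Three analysis sets fit the text: (a) all 40 children; (b) 'Other' set aside, with active and inactive pooled; (c) each class on its own. They do not estimate the same quantity.

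Reading (b) keeps a child only when symptoms and histology agree. Symptoms are one axis of the correlation, and histology is positively related to the other. The children removed are those most likely to count against an association. Reading (c) splits the sample and narrows the range of both variables.

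The third class is unlikely to be empty. Section 4.1 admits children with current, past or merely suspected EoE, and Section 2.1 acknowledges that symptoms track inflammation inconsistently. Class is known only after endoscopy, so an analysis set that is not fixed in advance could be chosen with data in hand.

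**Working it through.** **1. The plan's own figure.** Inputs from Section 10: correlation 0.45, 80% power, 5% significance (taken as two-sided), Spearman. The formula is n = v × [(1.960 + 0.842) / atanh(0.45)]² + 3, with atanh(0.45) = 0.4847, so the squared term is 33.41. With the Bonett-Wright variance for Spearman, v = 1 + 0.45²/2 = 1.10125, and n = 1.10125 × 33.41 + 3 = 39.8, so 40. The plan's figure reproduces, and power at n = 40 is 80.2%. (The Pearson version, v = 1, gives 37.)

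**2. Fewer children.** Power = Φ(√((n − 3)/1.10125) × 0.4847 − 1.960). The discordant share is not given. If 20%, 30%, 40% or 50% of the 40 are set aside, n is 32, 28, 24 or 20 and power is 70%, 64%, 56% or 48%. This ignores any bias from the selection.

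**3. Size of the selection effect under reading (b).** The documents give no EST-eosinophil correlation, symptomatic share, eosinophil-positive share or symptom cut-off, so all of these are assumed. Eosinophils, EST and PEESS are standard normal variables. The symptom status used for sorting is either PEESS itself or a variable correlated 0.6 with it. There are 40 children per trial and the test is two-sided at 5%.

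With no true EST-PEESS correlation, each cell gives Spearman and rejection rate for EST-eosinophil correlations of 0.5 / 0.7 / 0.9:

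| Symptomatic / eosinophil-positive | Mean kept of 40 | Sorting symptom is PEESS | Sorting symptom correlated 0.6 with PEESS |
|---|---|---|---|
| 50% / 50% | 20 | 0.35 / 0.50 / 0.66; 31 / 59 / 90% | 0.20 / 0.28 / 0.37; 12 / 21 / 34% |
| 70% / 60% | 22 | 0.24 / 0.34 / 0.46; 19 / 34 / 56% | 0.14 / 0.20 / 0.26; 9 / 14 / 21% |
| 90% / 60% | 23 | 0.09 / 0.13 / 0.17; 7 / 10 / 13% | 0.06 / 0.08 / 0.11; 6 / 7 / 8% |

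The numbers kept follow from independence under the null, for example 40 × (0.7 × 0.6 + 0.3 × 0.4) = 21.6. All 40 children, and the active group alone, give Spearman 0.00 and about 5% rejection. The inflation therefore comes from pooling the two concordant groups.

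**4. With a true correlation of 0.45** (Spearman 0.43), EST-eosinophil correlation 0.7, eosinophil-PEESS correlation 0.3 or 0.5, and the same cuts and symptom links (12 settings):

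| Analysis set | Children | Spearman | Rejection |
|---|---|---|---|
| (a) all | 40 | 0.43 | 80% |
| (b) active + inactive pooled | 22 to 27 | 0.41 to 0.71 | 52% to 98% |
| (c) active only | 11 to 23 | 0.21 to 0.37 | 11% to 39% |

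The 0.41 arises with 90% symptomatic, a symptom-PEESS link of 0.6 and an eosinophil-PEESS correlation of 0.5. In about half of the 12 settings, pooling rejects less often than the 80% from all 40.

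**The case against.** The strongest reply is that the documents never describe reading (b). A reader might infer from Section 4 that discordant children will be dropped, the rest pooled, and the primary result biased upward. The text does not support that. The separate-analysis sentence stands in the enrolment section, beside a sentence on matching, which makes sense for group comparisons and not for a one-sample correlation. Section 1.2.1 also speaks of experimental and control groups. The sentence may mean only an additional breakdown, with the correlations run on all 40; under that reading there is no bias and power is 80%. This stands, and it makes the warning conditional. It does not settle the matter, because no section limits the Section 4 rule to group comparisons.

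Nor is inflation universal. It appears in every null setting tried, but with a real correlation the pooled estimate can fall slightly below the true value and power can drop. The 90% rejection figure needs symptoms defined by PEESS itself, median splits and an EST-eosinophil correlation of 0.9. Section 4 refers to clinical symptoms and gives no PEESS cut-off, so that figure deserves little weight.

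Finally, the all-children analysis is unbiased in the simulation because the 40 are drawn from one population. Whether children who prove not to have EoE belong in the primary correlation is a choice of target population, and the sponsor should make it openly.

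**Conclusion.** The point holds as an unreconciled conflict that should be fixed, with a conditional warning about bias. Applied as written to the primary correlation, the Section 4 rule either selects on agreement between symptoms and histology or splits the sample. Neither gives an unbiased estimate with the stated 80% power at N=40.

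The direction of the null bias under pooling follows from the protocol's own statement that EST proteins track eosinophilia. Its size does not: the ranges above rest on assumed correlations, shares and cut-offs, and run from negligible to severe. The active group alone shows no upward bias, but it attenuates a real correlation. The matching sentence is a wording point with no quantified effect.

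**What to change.** - In Sections 4, 6.2 and 10, state that the primary EST-PEESS correlation and the other correlations use every child with an evaluable EST and the relevant outcome, whatever the post-endoscopy class.
- State that analyses by active, inactive and other are secondary or descriptive.
- If an EoE-only result is wanted, name it as secondary and define it by the diagnosis recorded before the study endoscopy, not by agreement between symptoms and histology.
- State that age and sex matching applies to group comparisons and removes no child from the correlations; Section 10 already provides for age and gender by regression.

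The cost is a few sentences, with no new data or patients. The wording should be settled before EST results are linked to outcomes.

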### **4.1 Subject Inclusion Criteria**

In order to be eligible to participate in this study, an individual must meet all of the following criteria:

- Provide signed and dated informed consent form.
- Willing to comply with all study procedures and be available for the duration of the study.
- Male or female, aged 7 to 18 years old, inclusive
- Undergoing upper Endoscopy with biopsy for clinical care at CHCO or CHOP
- Current or historical diagnosis of EoE, or suspected of having EoE

### **4.2 Subject Exclusion Criteria**

An individual who meets any of the following criteria will be excluded from participation in this study:

- Known connective tissue disease, other eosinophilic disorders
- Past history of caustic ingestion, esophageal surgery or other esophageal injury
- Known inflammatory bowel disease or esophageal motility disease (achalasia)
- Unwilling or unable to swallow the EST
- Oral or intravenous steroids in the preceding 60 days (not including swallowed topical fluticasone, budesonide, etc)
- Pregnancy
- Participation in a clinical study that may interfere with participation in this study

#### **4.3 Rationale for Study Population**

Based on prior experience with the EST in a similar population, one out of three subjects is unable to swallow the EST. In order to achieve the enrollment goal of 40 subjects completing all study procedures, 70 subjects would need to be consented at both CHCO and CHOP. It is anticipated that 35 subjects would sign consent at CHCO in order to reach 20 subjects completing the study.

#### **4.4 Strategies for Recruitment and Retention**

Potential participants will be screened from the clinical schedules at CHCO and CHOP. Should this method of recruitment yield poor accrual, the study teams will pursue other methods of recruitment including, but not limited to: print advertisement, social media and email communications. Research coordinators will contact the parents of the subjects and explain the study at least one week prior to the scheduled endoscopy. Interested potential participants will be scheduled for consenting and completion of the EST procedure. If the EST procedure cannot be completed prior to the Endoscopy with EndoFLIP, then the consent will be completed prior to the upper endoscopy and the EST procedure will be scheduled within one week of the Endoscopy. Subjects will receive reminder telephone calls prior to all scheduled procedures.

